## 9 ASSESSMENT OF INVESTIGATIONAL MEDICINAL PRODUCT

### 9.1 PRIMARY ENDPOINT

#### 9.1.1 Primary efficacy endpoint

Proportion of patients achieving sustained remission at Week 52. Sustained remission at Week 52 is defined by having met all of the following parameters:

1. Achievement of disease remission no later than Week 12

AND

2. Absence of disease flare from Week 12 through Week 52

AND

3. Sustained reduction of CRP (to  $<10$  mg/L, with an absence of successive elevations to  $\geq 10$  mg/L) from Week 12 through Week 52

AND

4. Successful adherence to the prednisone taper from Week 12 through Week 52.

Successful adherence to the prednisone taper may include the use of any excess prednisone (beyond the per protocol CS tapering regimen) with a cumulative dose of less than or equal to 100mg (or equivalent), such as those employed to manage an AE not related to PMR.

**Disease remission** is defined as resolution of signs and symptoms of PMR, and normalization of CRP ( $<10$  mg/L).

Note: A single CRP elevation ( $\geq 10$  mg/L) is not considered absence of remission unless CRP remains elevated ( $\geq 10$  mg/L) for two consecutive study visits.

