## **9.2 SECONDARY ENDPOINTS**

### **9.2.1 Secondary efficacy endpoints**

#### **9.2.1.1 Components of sustained remission composite measure at Week 52**

- Patients who achieved of disease remission by Week 12.
- Patients who have absence of disease flare from Week 12 through Week 52.
- Patients who have normalization of CRP (decrease to  $<10$  mg/L) with sustained normalization from Week 12 through Week 52.
- Patients who successfully adhere to the prednisone taper from Week 12 through Week 52.

Successful adherence to the prednisone taper may include the use of any excess prednisone (beyond the per protocol CS tapering regimen) with a cumulative dose of less than or equal to 100mg (or equivalent), such as those employed to manage an AE not related to PMR.

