#### **10.2.2.3 Visit 4-11 (Day 29±3 Week 4 to Day 281±3, Week 40)**

- Call IRT to register visit.

- Administer PRO questionnaires (EQ-5D-3L, FACIT-Fatigue, SF-36v2, HAQ-DI; Applicable only at **Visits 6 and 9**; at these visits PRO questionnaires should be completed prior to any significant interaction with the study team and prior to any physical examination or sampling).
- Review of concomitant medication.
- Dispense new patient diary and review last visit patient diary.
- Measure vital signs (including systolic and diastolic BP [mmHg], heart rate [beats per minute] and body temperature [°C]).
  - Measure body weight (kg) (Applicable only at Visits 6, 9 and 11)
  - Perform PMR clinical assessment for disease activity and flare.
  - Complete physician global assessment (MD-VAS) at Visits 6 and 9 only.
- Inquire about AEs/SAEs.
- Perform tuberculosis assessment.
  - Perform targeted physical examination (including head, eyes, ears, neck and throat, skin, respiratory, cardiovascular, neurologic, lymphatic examinations and abdominal examination) (**Applicable only at Visits 6, 9, and 11**).
  - Complete Glucocorticoid Toxicity Index questionnaire. (**Applicable only at Visits 6, 9 and 11**).
- Perform blood sampling at all visits (prior to administration of IMP) for the following tests:
  - CRP and ESR.
- Perform blood sampling (fasting, prior to administration of IMP) for the following tests: (**Applicable only at Visits 4, 6, 9 and 11**).
  - Hematology and chemistry.
  - Fasting lipids, fasting glucose and insulin.
  - HbA1c.
- Perform blood sampling (prior to administration of IMP) for the following tests: (**Applicable only at Visits 4, 6, 7, and 9**).
  - Serum sarilumab.  
**Note:** Additional sample is to be drawn 4-7 days after Visit 9 dosing. May be performed at the patient's home, if compatible with local organization.
- Perform blood sampling (prior to administration of IMP) for the following tests:
  - Anti-sarilumab antibody (Applicable only at Visits 6 and 9).
  - Biomarkers IL-6, sIL-6R. (Applicable only at Visits 6 and 9).
  - Immune Cell Phenotyping – Whole Blood (Applicable only at Visits 4 and 9).

- Future Use Samples – Plasma and Serum (Optional - requires separate signed consent form) (Applicable only at Visits 6 and 9).
- Perform urine pregnancy test (for WOCBP).
- Dispense and administer IMP.

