2.1.3 Efficacy endpoints

2.1.3.1 Primary efficacy endpoint(s)

The primary endpoint is the proportion of patients achieving sustained remission at Week 52, where the sustained remission at Week 52 is defined as having met all of the following parameters:

1. Achievement of disease remission not later than Week 12,
2. Absence of disease flare from Week 12 through Week 52,
3. Sustained reduction of CRP (to <10 mg/L, with an absence of successive elevations to ≥ 10 mg/L) from Week 12 through Week 52, and
4. Successful adherence to the prednisone taper from Week 12 through Week 52.

Components of primary endpoint are described as below:

1. Achievement of disease remission not later than Week 12

Disease remission is defined as resolution of signs and symptoms of PMR, and normalization of CRP (<10 mg/L). Note that a single CRP elevation (≥ 10 mg/L) is not considered absence of remission unless CRP remained elevated (≥ 10 mg/L) at the next study visit.

The status of normalization of CRP (<10 mg/L) will be determined based on the last two non-missing post-baseline CRP values measured up to Week 12. If at least one of them is <10 mg/L, then it is considered as normalization of CRP.

Signs and symptoms of disease

Evaluation of clinical signs and symptoms by the Efficacy Assessor at every study visit according to the schedule of assessment will include the following:

- Morning stiffness and/or pain, in the neck, shoulder and/or hip girdles
- Limited range of motion of the shoulders and/or hip girdles
- Constitutional symptoms, such as fatigue, weight loss and low-grade fever
- Other features judged by the clinician-investigator to be consistent with a PMR flare

The resolution of signs and symptoms of PMR is identified in eCRF “PMR Assessment” page with the question “Based upon the patient’s relevant medical history and the clinical assessment and responses provided above, does the patient have active PMR?” ticked as “No”. The resolution of signs and symptoms of PMR by Week 12 will be determined based on the last non-missing post-baseline PMR assessment measured up to Week 12.

Patients who took rescue CS due to active PMR prior to Week 12 or who permanently withdraw from the study treatment prior to Week 12 will be considered as not achieved disease remission by Week 12.

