Note that during the initial 12 weeks of prednisone taper, treatment for one flare before Week 12 is permitted if it can be successfully treated with a low dose (≤ 5 mg/day) prednisone add-on taper regimen (completed prior to Week 12) and provided that all other sustained remission parameters are met.

2. Absence of disease flare from Week 12 through Week 52.

Flare is defined as either 1) recurrence of signs and symptoms attributable to active PMR plus an increase in CS dose due to PMR, or 2) elevation of ESR attributable to active PMR plus an increase in CS dose due to PMR. Increase in CS dose is defined as:

- Any dose increase during the protocol defined steroid taper, or
- Re-initiation of prednisone therapy after the protocol defined taper has been completed.

Patients with disease flare are identified as those with the reason for treatment ticked “rescue therapy” in eCRF “Steroid Medication” page and to the question “If Rescue Therapy, please specify” ticked either “Active PMR” or “Elevated ESR Attributable to Active PMR”.

3. Sustained reduction of CRP (to <10 mg/L, with an absence of successive elevations to ≥10 mg/L) from Week 12 through Week 52

The status of normalization of CRP from Week 12 through Week 52 will be determined based on the CRP values measured at Week 16, Week 20, Week 24, Week 32, Week 40 and Week 52. If there are two or more consecutive visits with CRP ≥10 mg/L, then it is categorized as no normalization of CRP. Intermittent missing CRP at Week 16, Week 20, Week 24, Week 32, Week 40 or Week 52 will be imputed using last value carried forward (LOCF) approach up to the last non-missing measurement.

4. Successful adherence to the prednisone taper from Week 12 through Week 52

Successful adherence to the prednisone taper from Week 12 through Week 52 is defined as patients who did not take rescue therapy from Week 12 through Week 52 and any excess prednisone (beyond the per protocol CS tapering regimen) with a cumulative dose of ≤100 mg (or equivalent), such as those employed to manage AE not related to PMR. The cumulative dose of excess prednisone use will be counted from baseline to Week 52 (does not include add-on prednisone taken prior to Week 12).

In addition, patients who permanently withdraw from the study treatment prior to Week 52 will be considered as not having achieved component 2, 3, or 4 for the primary endpoint.

Blinding of CRP and ESR assessment results

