2.1.3.2 Secondary efficacy endpoint(s)

The following efficacy variables will be assessed:

- Components of sustained remission composite measure at Week 52
- Total cumulative corticosteroid (including prednisone) dose over during the treatment period
- Time to first PMR flare during the treatment period
- GTI Cumulative worsening score (CWS) and Aggregate improvement score (AIS) at Week 52.

Below are descriptions of these variables. Details related to imputation of GTI scores are described in [Section 2.5.2](#).

Components of sustained remission composite measure at Week 52

1. Proportion of patients who achieved disease remission by Week 12.
2. Proportion of patients who have no disease flare from Week 12 through Week 52.
3. Proportion of patients who have normalization of CRP (to <10 mg/L, with an absence of successive elevations to ≥ 10 mg/L) from Week 12 through Week 52.
4. Proportion of patients who successfully adhere to the prednisone taper from Week 12 through Week 52.

Total cumulative corticosteroid (including prednisone) dose during the treatment period

The total cumulative corticosteroid includes prednisone taper regimen per protocol, add-on prednisone prior to Week 12 or use of commercial prednisone during the study treatment period such as those employed to manage AE not related to PMR, and rescue corticosteroids dose prescribed for rescue therapy over the treatment period for PMR disease only.

Time to first PMR flare during the treatment period

The duration (in days) from randomization to first PMR flare after clinical remission and up to 52 weeks. Patients who never achieve remission will be censored at randomization day; and those who achieved clinical remission and never flared will be censored at the end of treatment assessment date up to Week 52.

The definition of PMR flare is provide in [Section 2.1.3.1](#) primary efficacy endpoint.

Clinical remission is defined as resolution of signs and symptoms and normalization of CRP (<10 mg/L). Intermittent missing CRP at visit will be imputed using last value carried forward (LOCF) approach. If missing signs and symptoms, then clinical remission is not achieved.

Glucocorticoid toxicity index (GTI) scores and components

The GTI is intended to capture glucocorticoid (GC)-related morbidity and GC-sparing ability of other therapies (2).

The GTI is composed of two components, the Composite GTI and the Specific List ([Table 2](#)).

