Appendix I Visit windows based on day ranges

Visit windows based on days relative to the first IMP dose will be used to map the efficacy, lab, vital signs, PK, and immunogenicity data to each scheduled visit (see [Table 7](#)).

Table 7 - Day range for each scheduled visit in the DB period for efficacy, lab, vital sign, PK and ADA summaries

Visit Label	Target Day	Schedule A ^a	Schedule B ^b	Schedule C ^c	Schedule D ^d	Schedule E ^e	Schedule F ^f	Schedule G ^g	Schedule H ^h	Schedule I ⁱ	Schedule J ^j
Double-Blind Period											
Baseline	1	≤ 1	≤ 1	≤ 1	≤ 1	≤ 1		≤ 1	≤ 1	≤ 1	≤ 1
Week 2	15	>1* - 21							>1* - 21	>1* - 49	
Week 4	29	22-42				>1* - 56	>1* - 56	>1* - 42	22 - 56		>1* - 98
Week 8	57	43-70						43 - 70			
Week 12	85	71-98	>1* - 126	>1* - 126		57 - 126	57 - 126	71 - 98	57 - 98	50 - 126	
Week 16	113	99-126						99 - 126	99 - 140		
Week 20	141	127-154						127 - 154			
Week 24	169	155-196	127 - 224	127 - 266		127 - 224	127 - 224	155 - 196	141 - 266	127 - 266	≥ 99
Week 32	225	197-252						197 - 252			
Week 40	281	253-322	225 - 322			225 - 322	225 - 322	253 - 322			
Week 52	365	≥323	≥ 323	≥ 267	>1*	≥ 323	≥ 323	≥ 323	≥ 267	≥ 267	

a Includes temperature, heart rate, blood pressure, PMR clinical assessments (including disease flare), CRP, ESR

b Includes weight, glucocorticoid toxicity index (excluding bone density assessment)

c Includes physician global assessments (MD-VAS), patient reported outcomes and antibodies to sarilumab/ADA

d Includes bone density assessment, ANA

e Includes hematology: hemoglobin, hematocrit, red blood cell (RBC) count and morphology (if RBC count is abnormal), white blood cell (WBC) differential, platelet count, absolute neutrophil count (ANC) and chemistry: sodium, potassium, calcium, chloride, bicarbonate, total protein, creatinine and clearance, blood urea nitrogen (BUN), uric acid, lactate dehydrogenase (LDH), phosphate, albumin, ALT (SGPT), AST (SGOT), alkaline phosphatase (ALP), total bilirubin, conjugated bilirubin, and unconjugated bilirubin

f Includes HbA1c, fasting glucose, fasting lipids: triglycerides (TG), total cholesterol, HDL, LDL

g Includes urine pregnancy test

h Includes serum sarilumab

i Includes biomarkers-IL-6 and sIL-6R

j Includes immune cell phenotyping (whole blood)

* Includes value measured on day 1 but after the first IMP dose

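### The SAP derives the CRP component of sustained remission without the Week 12 value, so two successive elevations at Weeks 12 and 16 are never tested

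*SAP*

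**What the plan says.** Protocol 9.1.1 defines the third component of sustained remission as a sustained CRP reduction "with an absence of successive elevations to" 10 mg/L or more, over Week 12 through Week 52. SAP 2.1.3.1 repeats this in the endpoint definition and in the heading of component 3.

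The SAP's derivation then says that the status "from Week 12 through Week 52 will be determined based on the CRP values measured at Week 16, Week 20, Week 24", and completes the list with Weeks 32, 40 and 52. Two or more consecutive visits at 10 mg/L or above is a failure.

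The Week 12 CRP enters component 1 only. There, normalization is judged "based on the last two non-missing post-baseline CRP values measured up to Week 12", and the SAP adds: "If at least one of them is <10 mg/L, then it is considered as normalization of CRP".

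The CRP component is also a secondary endpoint. Protocol 9.2.1.1 words it "with sustained normalization from Week 12 through Week 52"; SAP 2.1.3.2 words it "Proportion of patients who have normalization of CRP (to <10 mg/L, with an absence of successive elevations to" 10 mg/L or more, again from Week 12.

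The Week 12 value is available. For Visits 4 to 11 (Week 12 is Visit 6), Protocol 10.2.2.3 says "Perform blood sampling at all visits (prior to administration of IMP) for the following tests" and names CRP and ESR. SAP Appendix I gives Week 12 its own window (Days 71 to 98) under Schedule A, which "Includes temperature, heart rate, blood pressure, PMR clinical assessments (including disease flare), CRP, ESR".

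**The concern.** The definition starts at Week 12, but the first pair that the derivation can test is Week 16 with Week 20. Component 1 looks back from Week 12 and component 3 looks forward from Week 16, so the pair formed by Weeks 12 and 16 falls between them.

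No other rule picks it up. Flare depends on symptoms or ESR plus a corticosteroid increase. Post-baseline CRP is blinded to investigators, so it cannot prompt the rescue that would fail the patient by another route. The sensitivity analysis without acute phase reactants drops CRP altogether.

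At stake is agreement between the programmed primary endpoint and its protocol definition. One programmer working from the component heading and another from the visit list could obtain different responder counts. The secondary CRP component has the same gap, without the dilution by the other components.

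**Working it through.** **Scope.** The point turns on a definition, not on a sample-size figure. For completeness, the power table was recomputed (two-sided 0.05, 59 per group, no continuity correction): 95.6%, 91.2% and 87.0% for a 25-point difference, 98.9%, 97.3% and 95.4% for 30 points. The stated values are 95.6%, 91.2%, 86.9% and 98.8%, 97.2%, 95.4%. They do not depend on this issue.

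**Pattern count.** Code each visit as high (10 mg/L or more) or normal at Weeks 8, 12, 16, 20, 24, 32, 40 and 52, giving 2^8 = 256 complete patterns. The number of sequences with no two adjacent highs is 8 for four visits, 21 for six, 34 for seven and 55 for eight.

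| Rule | Patterns passing |
|---|---|
| Components 1 and 3 as written: Weeks 8 and 12 not both high (3 ways) × no adjacent highs in Weeks 16–52 (21) | 63 of 256 |
| Components 1 and 3 as defined: no adjacent highs in Weeks 8–52 | 55 of 256 |
| Component 3 alone as written: Week 12 free (2) × 21 | 42 of 128 |
| Component 3 alone as defined: no adjacent highs in Weeks 12–52 | 34 of 128 |

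The first two rows differ by 63 − 55 = 8. All 8 patterns are Week 8 normal, Weeks 12 and 16 high, Week 20 normal, with the 8 admissible continuations over Weeks 24 to 52. These are counts of patterns, not proportions of patients.

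**Patients reclassified on the CRP criteria, before the other components.** Assume an independent chance p of elevation at each visit. For components 1 and 3 together the share is p²(1−p)² × P, where P = (1−p)⁴ + 4p(1−p)³ + 3p²(1−p)² is the chance of no adjacent highs in Weeks 24 to 52. For component 3 alone, divide by (1−p), because Week 8 no longer matters.

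| Assumed p | Both CRP criteria | Of 59 | Component 3 alone, of 59 |
|---|---|---|---|
| 5% | 0.2% | 0.1 | 0.1 |
| 10% | 0.8% | 0.5 | 0.5 |
| 20% | 2.3% | 1.4 | 1.7 |
| 30% | 3.5% | 2.0 | 2.9 |

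**Effect on the composite.** Let f be the share of counted responders who have the pattern. Wrongly counted responders = 59 × response rate × f. For placebo, with f assumed at 1% to 5% and the planned rates of 5% to 15%: 59 × 0.05 × 0.01 = 0.03, up to 59 × 0.15 × 0.05 = 0.44.

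**Illustration by arm (all rates assumed).** Take a two-state Markov chain. On placebo, P(high after normal) is 0.10, 0.15 or 0.20 and P(high after high) is 0.5, so 17% to 29% of visits are elevated. On sarilumab, P(high after normal) is 0.01 and P(high after high) is 0.2 or 0.5, so 1% to 2% are elevated.

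- Placebo: f is 2.55%, 3.85% or 5.16%. Wrongly counted: 59 × 0.05 × 0.0255 = 0.08 to 59 × 0.15 × 0.0516 = 0.46.
- Sarilumab, at 30% to 40% response: f is 0.16% or 0.25%. Wrongly counted: 59 × 0.30 × 0.0016 = 0.03 to 59 × 0.40 × 0.0025 = 0.06.
- With a true 25-point difference and Fisher's exact test at 0.05, correcting the rule changes the decision to significant in 0.3% to 2.7% of trials and to non-significant in 0.05% to 0.23%.

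**Direction.** The omission adds more responders on placebo when f on placebo exceeds f on sarilumab by more than the ratio of response rates: 30/5 = 6.0, 35/10 = 3.5 or 40/15 = 2.7. The assumed chains give ratios of 2.55/0.25 = 10 to 5.16/0.16 = 32.

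**The case against.** The best reply is that Week 12 belongs to component 1, so component 3 properly starts at the next visit. The SAP does not say so. Its note under component 1 excuses a single elevation unless CRP is still elevated at the next visit. For a Week 12 elevation that visit is Week 16, which component 1 never examines. SAP 1.6 also says that the efficacy analyses are unchanged from the protocol.

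A second objection concerns the repair. Component 3 fills intermittent missing CRP by carrying the last value forward. Once Week 12 is on the list, a patient elevated at Week 12, missing at Week 16 and normal at Week 20 could fail on one measured elevation. That is true, but the SAP already treats every later pair this way (for example Week 16 high and Week 20 missing). It is a reason to state the rule, not to leave Week 12 out.

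A third objection is that the effect is tiny, the rates are invented and the CRP-free sensitivity analysis is already planned. This largely stands. The modelled figures show only an order of magnitude. A stationary chain also ignores that, between Weeks 12 and 14, Group 1 prednisone runs from 2 mg to none while Group 2 stays at 8 mg (Protocol Appendix A).

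**Conclusion.** The concern holds and is minor. As written, the derivation passes some patients whom the protocol and SAP definitions fail. The textual finding and the pattern counts need no assumption.

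The size does rest on assumptions, because the documents give no CRP rates. On the ranges shown, fewer than half a responder of 59 per arm is wrongly counted in the composite. The calculation treats CRP as independent of the other components. Protocol section 4 links persistently raised CRP to relapse, so many of these patients would fail anyway and the true effect is likely smaller. The descriptive CRP component could move by more, up to about 3 of 59 if 30% of visits were elevated.

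SAP 2.4.4.1 acknowledges sarilumab's effect on acute phase reactants, so elevations should be commoner on placebo. The error then probably works against showing superiority. The supporting ratio of f between arms is modelled, not documented. A reversal from significant to non-significant is possible but very unlikely, so this point does not put a positive result in doubt.

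**What to change.** In SAP 2.1.3.1, component 3, change the visit list to Weeks 12, 16, 20, 24, 32, 40 and 52, so that CRP of 10 mg/L or more at both Weeks 12 and 16 is a failure. Use the same derivation for the secondary CRP component in SAP 2.1.3.2 and 2.4.4.2. In the same sentence, state whether the Week 12 value may be carried into a missing Week 16, and what happens if Week 12 itself is missing.

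The cost is a small text change and one more visit in the derivation program; no new data or analyses are needed. SAP 1.1 gives the last patient's last visit as 19 May 2021 and SAP section 4 puts database lock about four weeks later, so the change should be made before lock and while blinded. If lock has passed, report the responder counts under both derivations.

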2.1.3.2 Secondary efficacy endpoint(s)

The following efficacy variables will be assessed:

- Components of sustained remission composite measure at Week 52
- Total cumulative corticosteroid (including prednisone) dose over during the treatment period
- Time to first PMR flare during the treatment period
- GTI Cumulative worsening score (CWS) and Aggregate improvement score (AIS) at Week 52.

Below are descriptions of these variables. Details related to imputation of GTI scores are described in [Section 2.5.2](#).

Components of sustained remission composite measure at Week 52

1. Proportion of patients who achieved disease remission by Week 12.
2. Proportion of patients who have no disease flare from Week 12 through Week 52.
3. Proportion of patients who have normalization of CRP (to <10 mg/L, with an absence of successive elevations to ≥ 10 mg/L) from Week 12 through Week 52.
4. Proportion of patients who successfully adhere to the prednisone taper from Week 12 through Week 52.

Total cumulative corticosteroid (including prednisone) dose during the treatment period

The total cumulative corticosteroid includes prednisone taper regimen per protocol, add-on prednisone prior to Week 12 or use of commercial prednisone during the study treatment period such as those employed to manage AE not related to PMR, and rescue corticosteroids dose prescribed for rescue therapy over the treatment period for PMR disease only.

Time to first PMR flare during the treatment period

The duration (in days) from randomization to first PMR flare after clinical remission and up to 52 weeks. Patients who never achieve remission will be censored at randomization day; and those who achieved clinical remission and never flared will be censored at the end of treatment assessment date up to Week 52.

The definition of PMR flare is provide in [Section 2.1.3.1](#) primary efficacy endpoint.

Clinical remission is defined as resolution of signs and symptoms and normalization of CRP (<10 mg/L). Intermittent missing CRP at visit will be imputed using last value carried forward (LOCF) approach. If missing signs and symptoms, then clinical remission is not achieved.

Glucocorticoid toxicity index (GTI) scores and components

The GTI is intended to capture glucocorticoid (GC)-related morbidity and GC-sparing ability of other therapies (2).

The GTI is composed of two components, the Composite GTI and the Specific List ([Table 2](#)).

The Composite GTI consists of nine domains (body mass index (BMI), glucose tolerance, blood pressure, Hyperlipidemia, Bone Health (BMD), steroid myopathy, Skin steroid-related Toxicity, Neuropsychiatric – steroid related symptoms and infection) on common steroid-related adverse events anticipated to occur in $\geq 5\%$ of patients treated in a clinical trial involving glucocorticoids. The Specific List consists of 23 items (11 domains) that are mainly less common but serious adverse effects, serving as a complementary tool to the Composite GTI to ensure that all important elements of glucocorticoid toxicity were captured.

The domains of the Composite GTI and the specific list of the GTI will be assessed at baseline, Week 12, Week 24, Week 40 and Week 52, except for bone density (BMD) which will be assessed at Baseline and Week 52 only.

For patients who withdraw from the study prior to Week 24, BMD will not be measured at the EOT visit as no substantial changes are expected within 6 months of treatment. As a result, missing BMD score will be imputed as 'no change'. The BMD measured at the end of treatment (EOT) visit will be included in the definition of cumulative GTI scores (i.e., CWS and AIS as defined below) at Week 52 regardless when the EOT visit occurred.

Scoring of the Glucocorticoid Toxicity Index (GTI)

Domain-specific score for each patient at a visit is defined as the weight assigned based on the change in severity level as described for each domain in [Table 2](#).

Composite GTI score for each patient at a visit is the sum of 9 domain-specific scores at each visit.

Cumulative GTI score is the sum of composite GTI score across visits. Two cumulative GTI scores, CWS and AIS, will be defined.

- **Cumulative worsening score (CWS)**

CWS is designed to assess cumulative GC toxicity, regardless of whether the toxicity has lasting effects or is transient. New toxicities that occur are added, but toxicities that appear to resolve on follow-up are not removed. Thus, the CWS serves as a lasting record of GC toxicity observed and can only increase or remain the same over time.

CWS will be lower in the treatment arm compared to the placebo arm at the end of trial, if the treatment is effective at decreasing GC toxicity over time.

- **Aggregate improvement score (AIS)**

Patients are anticipated to have some GC toxicity at baseline, the AIS would be important in establishing that the new therapy is effective at diminishing any baseline GC toxicity over time. With the AIS, toxicities can be removed if improvement occurs, and added if worsening occurs.

AIS decrease over time means that the treatment is effective in decreasing GC toxicity level, compared to placebo which may show fluctuation of CIS over time. Negative score reflects that toxicities present at baseline (or occurring during the trial) resolved over the treatment period.

The steps to calculate the CWS and AIS at Week 52 are described below.

Step 1: Calculate domain-specific worsening score (for computing CWS in Step 2) and improvement score (for computing AIS in Step 2) at each visit.

For Domains without sub-items (Body Weight, Glucose Metabolism, Blood Pressure, Lipid Metabolism, Bone Health and Steroid Myopathy),

- a) For worsening score, only consider positive domain-specific score at each visit. For domain with a negative domain-specific score, the worsening score will be 0.

- b) For improvement score, all domain-specific scores (could be positive or negative) at each visit will be considered.

The Skin and Neuropsychiatric domains both have sub-items. For the Skin domain, these are Acneiform Rash, Easy Bruising, Hirsutism, Atrophy/Striae, and Erosions/tears/ulcerations. For the Neuropsychiatric domain, these are Insomnia, Depression, Mania, and Cognitive Impairment.

- a) For worsening score, only the item with the highest weight is scored for any GTI interval (typically three months) with the CWS. As an example, if neither insomnia nor depression were present at the baseline visit but there is now mild Insomnia and moderate depression present at follow-up, then only the moderate depression is scored (+63 points).
- b) For improvement score, improvement as well as worsening can be recorded. Because it is conceivable that one item might improve while another worsens, the item of greatest improvement (highest absolute weight) and the item of greatest worsening (highest weight) are recorded for given GTI interval.

For Infection Domain, the worsening score and improvement score handle the scoring of infections differently, because the CWS and AIS reflect reciprocal measures of GC toxicity.

- a) For worsening score, the most severe infection in every GTI interval is scored.
- b) For improvement score, only the most severe infection occurring over the course of the entire trial is scored.

Step 2: Calculate composite worsening score and improvement score at each visit by summing the 9 domain-specific score.

- a) For composite worsening score, sum the 9 domain-specific worsening scores.
- b) For composite improvement score, sum the 9 domain-specific improvement scores.

Step 3: Calculate cumulative GTI scores by summing composite scores across visits.

- a) For CWS at Week 52, summing composite GTI worsening score at Week 12, Week 24, Week 40, and Week 52.
- b) For AIS at Week 52, summing composite GTI improvement score at Week 12, Week 24, Week 40, and Week 52.

Table 2 – The Glucocorticoid Toxicity Index

Composite GTI	Item weight	Specific List¹
1.BMI		
Decrease by \geq 5 BMI units	-36	Major increase in BMI
Decrease by >2 but <5 BMI units	-21	
No significant change (\pm 2 BMI units)	0	
Increase of >2 to <5 BMI units	21	
Increase of 5 or more BMI units	36	

Composite GTI	Item weight	Specific List¹
2.Glucose tolerance		
Improvement in HbA1c AND decrease in medication	-44	Diabetic retinopathy
Improvement in HbA1c OR decrease in medication	-32	Diabetic nephropathy
No significant change	0	Diabetic neuropathy
Increase in HbA1c OR increase in medication	32	
Increase in HbA1c AND increase in medication	44	
3.Blood pressure		
Improvement in BP AND decrease in medication	-44	Hypertensive emergency
Improvement in BP OR decrease in medication	-19	Posterior reversible encephalopathy syndrome
No significant change	0	
Increase in BP OR increase in medication	19	
Increase in BP AND increase in medication	44	
4.Hyperlipidemia		
Decrease in LDL AND decrease in medication	-30	
Decrease in LDL OR decrease in medication	-10	
No significant change	0	
Increase in LDL OR increase in medication	10	
Increase in LDL AND increase in medication	30	
5.Bone Health (BMD)		
Increase in BMD (gain of more than 3%)	-29	Major decrease in bone density
No significant change in BMD (+/- 3%)	0	Insufficiency fracture
Decrease in BMD (loss of more than 3%)	29	
6.Steroid myopathy		
Moderate weakness to none	-63	Severe steroid myopathy
Moderate to Mild weakness	-54	
Mild weakness to none	-9	
No significant change	0	
None to Mild weakness (without functional limitation)	9	
Mild to Moderate weakness	54	
None to Moderate weakness (with functional limitation)	63	
7.Skin steroid-related Toxicity		
Decrease in Skin Toxicity – Moderate to None	-26	Severe skin toxicity
Decrease in Skin Toxicity – Moderate to Mild	-18	
Decrease in Skin Toxicity – Mild to None	-8	
No significant change	0	
Increase in Skin Toxicity – None to Mild	8	
Increase in Skin Toxicity – Mild to Moderate	18	
Increase in Skin Toxicity – None to Moderate	26	
8.Neuropsychiatric – steroid related symptoms		
Decrease in NP Toxicity – Moderate to None	-74	Psychosis
Decrease in NP Toxicity – Moderate to Mild	-63	GC-induced violence
Decrease in NP Toxicity – Mild to None	-11	

Composite GTI	Item weight	Specific List¹
No significant change	0	Other severe neuropsychiatric symptoms
Increase in NP Toxicity – None to Mild	11	
Increase in NP Toxicity – Mild to Moderate	63	
Increase in NP Toxicity – None to Moderate	74	
9.Infection		
No infection	0	Grade IV infection
Oral or vaginal candidiasis or non-complicated zoster (<Grade3)	19	Grade V infection
Grade 3, 4, or 5 infection	93	

¹ Maximum weight is given for specific list events in Blood pressure, Steroid myopathy, Skin toxicity, Neuropsychiatric and Infection domains at each visit. For the rest of domains, specific list events will not affect the corresponding domain specific score.

